10.3 Abnormal Laboratory Values

A clinical laboratory abnormality should be documented as an adverse event if the abnormality is of a degree, typically at least grade 2 and not present as grade 1 or better at baseline, that requires active management; e.g. change of dose, discontinuation of the drug, more frequent follow-up assessments, further diagnostic investigation.

10.4 Hospitalization, Prolonged Hospitalization or Surgery

Any adverse event that results in hospitalization or prolonged hospitalization should be documented and reported as a serious adverse event unless specifically instructed otherwise in this protocol. Any condition responsible for surgery should be documented as an adverse event if the condition meets the criteria for an adverse event.

Neither the condition, hospitalization, prolonged hospitalization, nor surgery are reported as an adverse event in the following circumstances:

-Hospitalization or prolonged hospitalization for diagnostic or elective surgical procedures for a preexisting condition. Surgery should not be reported as an outcome of an adverse event if the purpose of the surgery was elective or diagnostic and the outcome was uneventful.

-Hospitalization or prolonged hospitalization required to allow efficacy

measurement for the study.

-Hospitalization or prolonged hospitalization for therapy of the target disease of the study, unless it is a worsening or increase in frequency of hospital admissions as judged by the clinical investigator.

10.5 Recording of Adverse Events

At each contact with the patient, the investigator must seek information on adverse events by specific questioning and, as appropriate, by examination. Information on all adverse events should be recorded immediately in the source document, and also in the appropriate adverse event module of the case report form (CRF). All clearly related signs, symptoms, and abnormal diagnostic procedures results should be recorded in the source document, though should be grouped under one diagnosis. All adverse events occurring during the study period must be recorded. The clinical course of each event should be followed until resolution, stabilization, or until it has been determined that the study treatment or participation is not the cause. Serious adverse events that are still ongoing at the end of the study period must be followed up to determine the final outcome. Any serious adverse event that occurs after the study period and is considered to be possibly related to the study treatment or study participation should be recorded and reported immediately.

10.6 Reporting of Adverse Events and Serious Adverse Events

10.6.1 Study Chair Notification by Investigator

A serious adverse event must be reported to the Study Chair within 24 hours of a member of the study team becoming aware of the event.

Report serious adverse events by phone and facsimile to:

[name], MSCE, or via the HUP page operator

At the time of the initial report, the following information should be provided:

- Study identifier
- Study Center
- Patient number
- A description of the event
- Date of onset
- Current status
- Whether study treatment was discontinued
- The reason why the event is classified as serious
- Investigator assessment of the association between the event and study

treatment

[contact]

10.6.2 IRB Notification by Investigator-sponsor

Reports of all serious adverse events (including follow-up information) must be submitted to the IRB and CTSRMC (Penn) within 10 working days, according to IRB guidelines.

Reporting Process to IRB at Penn: Principal Investigators are encouraged to submit reports of unanticipated problems posing risks to subjects or others using the form: "Unanticipated Problems Posing Risks to Subjects or Others Including Reportable Adverse Events" via HS-ERA or a written report of the event (including a description of the event with information regarding its fulfillment of the above criteria, follow-up/resolution and need for revision to consent form and/or other study documentation) within 7 working days and the PI or her designee will enter the event into HS-ERA and VELOS for Penn and participating sites. Participating sites should follow local, institutional guidelines on Event Reporting.

For reportable deaths, the initial submission to the IRB may be made by contacting the IRB Director or designee at [contact]. All deaths will be reported via HS-ERA, as well.

10.6.3 FDA Notification by Investigator-sponsor

This study is IND exempt and reporting to the FDA is voluntary using a Medwatch 3500 or via the FDA's website for voluntary reporting.

10.6.4 Abramson Cancer Center DSMC notification

All adverse events meeting the ACC'S DSMC reporting requirements outlined below will be reported to the ACC DSMC through the PennCTMS (Velos) Clinical Trial Management System AE/SAE Form.

- All Grade 3 or higher adverse events regardless of attribution or expectedness must be submitted to the ACC'S DSMC **within 10 business days** of knowledge.
- All unexpected deaths must be reported **within two business days** of knowledge. Deaths related to disease progression must clearly state that fact.
- All others deaths must be reported **within 30 days** of knowledge. Deaths of subjects greater than 90 days from the last study treatment/intervention are not reportable.

All AE/SAEs should include grade, attribution and expectedness as determined by the PI or sub-I. Only an investigator may determine the attribution and expectedness.

For attributions of "unrelated", an alternative explanation must be provided to explain to what the event is being attributed.

For studies using multiple agents in a single study, the agent to which the event is being attributed should be identified.

Every effort should be made to report an event as a diagnosis, not as a list of symptoms. Symptoms that led to the diagnosis should be included in the event description, but should not be the actual event.

10.6.5 IND SAFETY UPDATES/ALERTS

All IND Safety Updates/Alerts (sent by investigators) with a grade 3 or higher, regardless of attribution or expectedness must be submitted to the DSMC within 30 days. Reports should be sent to the DSMC for 6 months from the date the last Penn

subject was treated.

Although this protocol is IND-exempt, it is the responsibility of each PI to notify all participating investigators, in a written safety report using an IND safety report template, of any adverse event associated with the use of the drug that is both serious and unexpected, as well as any finding from tests in laboratory animals that suggest a significant risk for human subjects. Additionally, investigators are also required to identify in IND safety reports all previous reports concerning similar adverse events and to analyze the significance of the current event in light of the previous reports. Reports will be sent, via e-mail to participating sites, for review and forwarding to their internal committees, as appropriate.

SAE Definition.

10.6.6 Novartis instructions for rapid notification of serious adverse events

1. The principal investigator has the obligation to report all serious adverse events to the FDA, IRB, and Novartis Pharmaceuticals Clinical Safety and Epidemiology Department (CS&E).

2. All events reported to the FDA by the investigator are to be filed utilizing the Form FDA 3500A (MedWatch Form).

3. All events must be reported, by [contact]), to Novartis Pharmaceuticals CS&E Department within 24 hours of learning of its occurrence. This includes serious, related, labeled (expected) and serious, related, unlabeled (unexpected) adverse experiences. All deaths during treatment or within 30 days following completion of active protocol therapy must be reported within 5 working

days.

4. Any serious adverse event occurring after the patient has been administered one dose of study drug until 4 weeks after the patient has stopped study participation must be reported. This includes the period in which the study

protocol interferes with the standard medical treatment given to a patient (e.g. treatment withdrawal during washout period, change in treatment to a fixed dose of concomitant medication).

5. Serious adverse events occurring more than 30 days after study discontinuation need only be reported if a relationship to the Novartis study drug (or therapy) is suspected.

10.7 Internal Safety and Compliance Entities

The Data Safety and Monitoring Committee (DSMC) of the University of Pennsylvania's Abramson Cancer Center will monitor the data quality and adherence to safety rules. Additionally, the DSMC will review all safety/toxicity data for the trial and recommend trial suspension or termination as needed. Specific details of monitoring and audit frequency will be included in the Monitoring Plan, but will be at least every 6 months.

Patients will be evaluated for toxicity if they have received at least one dose of HCQ.

The timely reporting of adverse events (including toxic deaths) is required by the Food and Drug Administration. The reporting of toxicities is part of the data reporting for this study.

10.8 Medical and Research Monitoring

It is the responsibility of the Principal Investigator to oversee the safety of the study at his/her site. This safety monitoring will include careful assessment and appropriate reporting of adverse events, as noted above, as well as the construction and implementation of a site data and safety monitoring plan. Medical monitoring by an independent clinician within the Department of Medicine, Division of Hematology-Oncology will include a regular assessment of the number and type of serious adverse events on a periodic basis. [name] [name] is a board certified oncologist, and a member of the solid malignancies clinical trials group at UPENN. She is the PI on multiple phase I/II trials. The medical monitor will meet with [name] and clinical research staff quarterly. She will review adverse events, response assessments, and decisions related to modifications.

Furthermore, [name] will serve in the role of independent research monitor. The roles/responsibilities of the independent research monitor are outlined below. It is noted that [name] has no apparent conflict of interest and as the independent research monitor, she is not under the supervision of the PI or other investigators or research staff.

The research monitor:

- may discuss the research protocol with the investigators, interview human subjects, and consult with others outside of the study about the research;
- shall have authority to stop a research protocol in progress, remove individual human subjects from a research protocol, and take whatever steps are

- necessary to protect the safety and well-being of human subjects until the IRB can assess the monitor's report;
- shall have the responsibility to promptly report their observations and findings to the IRB or other designated official and the Human Research Protection Office (HRPO) of the US Army Medical Research and Material Command (USAMRMC)

10.9 Study Monitoring Plan

This study will be monitored by the Principal Investigator and sub-investigators, as appropriate. Such monitoring will include at least weekly meetings of the study team to review accrual, toxicity, SAEs, dose escalations and study finding. In addition, the PI will ensure that data are completed in a timely manner and he or his designee will periodically review the data for accuracy, completeness and integrity.

10.10 Auditing and Inspecting

The investigators will permit the Cancer Center's Administrative Director of Compliance and Auditing or her designee to review records, data and facilities at mutually agreeable times.

This study will be audited by the Department of Compliance and Monitoring (DOCM) as a high-risk study. Auditing will occur 6 months after the first subject enrolls and every six months thereafter until the study terminates. Audits will be scheduled approximately 5 weeks in advance of the audit. Lack of cooperation with scheduling will result in the study being put on hold at the participating sites until an audit is conducted. The DOCM may at its discretion, modify the audit schedule or the audit process.

10.11 Data Safety Monitoring Board

In addition to the above safeguards, an independent data safety monitoring committee, consisting of 2 medical oncologists and a member of the patient advocate team will meet with the PI and the study team monthly to review safety data, to assure that no unanticipated safety signals or risks are arising in the conduct of the study. In addition, the DSMB will review interim safety analyses for each arm after every 3 patients have been enrolled. We will implement a Bayesian toxicity monitoring approach with a target protocol-defined DLT rate of 30% as outlined in the statistical plan. This additional safeguard is to ensure that patients on this trial, with potentially curable disease, are being monitored closely.

10.12 Protocol Deviations and Exception Requests

A protocol deviation is a one time, unintentional action or process that departs from the IRB and DSMC approved study protocol, involving one incident and identified retrospectively, after the event occurred. If the impact on the protocol disrupts the study design, may affect the outcome (endpoints) or compromises the safety and welfare of the subjects, the deviation is considered "major" and must be reported to the DSMC and the IRB within 10 business days.

Deviations must be submitted if they:

- have the potential to adversely affect subject safety
- increase risks to participants

- adversely affect the integrity of the data
- violate the rights and welfare of participants
- affect the subject's willingness to participate in research

Other minor deviations should be explained in a memo to file or on a deviation log and summarized at continuing review.

If there is a planned deviation from the protocol, the situation will be submitted to the IRB and DSMC PRIOR to the event as an exception request, and approval will be sought before implementation. Exceptions to eligibility, treatment/dosing, contraindicated treatment/therapies/ interventions or safety tests for investigator-initiated treatment studies may be rejected by the ACC DSMC. Exception requests must provide strong and compelling scientific and clinical information as well as a statement explaining whether or not the protocol will be amended. If the protocol will not be amended a rationale must be provided. A protocol amendment is required if this situation is likely to recur. Study PI and Medical Monitor approval must be obtained prior to submitting an exception request.

11 MEASUREMENT OF EFFECT

For the purposes of this study, patients should be re-evaluated for response per the study calendar.

11.1 Definitions

11.1.1 Evaluable for toxicity

All patients will be evaluable for toxicity from the time of their first treatment with HCQ, EVE or both.

11.1.2 Evaluable for objective response

Only those patients who have measureable DTCs present at baseline, have received at least one cycle of therapy, and have had their disease re-evaluated at the 24 week timepoint will be considered evaluable for response. These patients will have their response classified according to the definitions stated below. We will report on both the "intent-to-treat" population and the evaluable population per the above criteria in order to fully determine whether the interventions are both feasible and showing sufficient evidence of activity to take forward to a larger phase III trial powered for relapse-free survival (RFS).

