2.2 Secondary Clinical Objectives

2.2.1 To determine the safety of administering HCQ + EVE in combination with adjuvant endocrine therapy

Endpoints

- Incidence of adverse events within each treatment stratum and dose level by NCI CTCAE v4 criteria.

2.2.2 To evaluate preliminary efficacy of HCQ, EVE or the combination in reducing or eliminating DTCs

Endpoints

- Change in bone marrow DTCs at 3, 6 and 12 months of treatment relative to baseline (pre-treatment)
- Change in bone marrow DTCs at 3 months with no treatment (Arm D Control) compared to any treatment (Arms A, B or C)
- Incremental benefit of an additional 6 months of therapy in patients who have DTCs after initial 6 months of therapy
- Incremental benefit of combination therapy compared to single-agent therapy

2.2.3 To estimate the risk of recurrence after treatment with HCQ, EVE, or the combination

Endpoint

- 3-year recurrence free survival (RFS)

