5. Bone marrow aspirate performed at the end observation (before the start of therapy), at the end of C3 (between D23-28), at the end of C6 (between D23-21 days after last dose IP therapy), and, if patient continued on additional treatment, at the end of C12, (between D23-21 days after last dose IP therapy).
6. Blood collected for ptDNA and CTCs pretreatment and at the completion of observation (before the start of therapy), at the completion of C3 (before the start of C4), at the completion of C6 (within 21 days of last dose), and at completion of C12 (within 21 days of last dose).
7. Baseline bone marrow aspirate positive for DTCs must have been done within 6 months of the screening phase.
8. Participants who clear DTCs from the bone marrow (i.e., negative DTC-IHC test) after 6 or 12 cycles of therapy will have optional bone marrow aspirate collected for retesting at the first 6 month follow up visit.

Note: Additional tests may be performed at the discretion of the treating investigator as clinically indicated. The sample collection schedules outlined above are based on an ideal subject. The sample schedule should be followed as closely as is realistically possible; however, the schedule may be modified due to problems such as scheduling delays or conflicts (e.g., clinic closure, poor weather conditions, vacations, etc.)

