7.8 Discontinuation of Treatment

Patients who discontinue study treatment prior the final planned dose will enter the follow up phase, and complete all procedures and follow-up dictated by the protocol. Patients who choose to discontinue all study participation, including follow-up, may do so at any time without penalty, by following the procedures outlined in section 7.11. At the time of any treatment discontinuation or withdrawal, site research staff should document the reasons and conditions under which discontinuation of treatment occurred and whether the patient is willing to continue follow up or will be requesting full withdrawal from the study. Each subject has the right to discontinue study treatment or withdraw from the overall study at any time without prejudice. The investigator may discontinue any subject's participation for any reason, including adverse event or failure to comply with the protocol. Because this is a randomized pilot trial following intent-to-treat principals, patients who discontinue study treatment will be followed for study outcomes as outlined in the protocol. Reasons for withdrawal from study treatment include the following:

- Delay in treatment > 28 days due to treatment-related toxicity or major event (if due to treatment-related toxicity, patient will be taken off the treatment that is most likely to be related to the toxicity).
- Disease Recurrence: Remove patient from protocol therapy at the time progressive disease is documented.
- Extraordinary Medical Circumstances: If at any time the treating physician feels constraints of this protocol are detrimental to the patient's health remove the patient from protocol therapy.
- Patient's refusal to continue treatment: In this event, document the reason(s) for withdrawal.
- Failure to comply with protocol (as judged by the investigator such as compliance below 80%, failure to maintain appointments, etc.).

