12.2.2 Secondary Endpoints

The secondary endpoints are tolerability/toxicity and the measured effect of the investigational therapy on DTCs in patients with measureable DTCs at baseline and the comparison of this effect to that in a control population. Because this is proof-of-concept, sample sizes are not sufficient to address long-term recurrence risk. Randomization is being performed to minimize uncontrolled confounding.

We will define “response” for each patient as a 50% or greater decrease in DTC number at each treatment time point compared to baseline. A treatment arm will be considered successful if at least 3 of 15 patients experience this predefined response endpoint. This strategy is being used to provide preliminary estimates of effect on DTCs and to assess whether one or more treatment approaches has sufficient activity to be considered in a larger study powered for relapse-free survival. We anticipate that the baseline variability in DTC measurement will lead to no more than a 4% response rate in the absence of treatment (null rate). While the trial is powered for feasibility, 15 patients provide approximately 80% power to detect a response rate of 20%, warranting further study of the treatment strategy evaluated in this patient population and clinical setting.

We will also estimate, within each treatment group, the % change in BM-DTC number, defined as the difference between BM-DTCs enumerated at 6 months and at baseline, divided by the number at baseline; we will compare this quantity across treatment groups using simple regression analyses with indicator variables for the three active treatments compared to the delayed treatment. While the trial is powered for feasibility, rather than detection of change in BM-DTCs across treatment group, 15 patients per group will provide 80% power (using a two-group t-test with a two-sided alpha level of 0.05) to detect a decrease in BM-DTCs of approximately 1 standard deviation between any two groups and will provide important preliminary data for designing future trials.

Because of tumor heterogeneity, the natural history of recurrence varies substantially between breast cancer subtypes. We have elected not to expand the

sample size to evaluate subtypes individually in this feasibility pilot, but expect that we will enroll a mix of patients across subtypes that will shed light on variability in DTCs by subtype in an exploratory fashion.

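### One 24-week evaluability rule covers every DTC time point, so evaluable 3-month results, including untreated Arm D, depend on what happens after 3 months

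*Protocol*

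**What the plan says.** Protocol section 11.1.2 opens with an exclusive condition, "Only those patients who have measureable DTCs present at baseline", and then adds that they must "have received at least one cycle of therapy, and have had their disease re-evaluated at the 24 week timepoint". It makes no distinction by visit and no exception for untreated controls. The same section promises results for the intent-to-treat "population and the evaluable population per the above criteria", and it uses both to judge whether there is enough activity to go on to phase III.

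The endpoints are not confined to 24 weeks. Section 12.2.2 defines response as a "50% or greater decrease in DTC number at each treatment time point compared to baseline", and section 2.2.2 lists "Change in bone marrow DTCs at 3 months with no treatment (Arm D Control) compared to any treatment" as an endpoint. Sections 5.3 and 7.1 place the Arm D control marrow at the end of 12 weeks of observation, before any study drug.

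On early stopping, section 7.8 states "Patients who discontinue study treatment prior the final planned dose will enter the follow up phase", and the sentence goes on to say that they complete whatever the protocol requires. Section 5.3 ties the 24-week marrow to the end of cycle 6. In the follow-up phase, Table 2 lists only an optional marrow, for "Participants who clear DTCs from the bone marrow (i.e., negative DTC-IHC test) after 6 or 12 cycles of therapy".

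The SAP models DTC counts by visit for each patient and expresses treatment effects against observation at C3. The SAP text available names no analysis population.

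**The concern.** A 3-month result is complete once the baseline and 3-month marrows have been read. Under section 11.1.2 it counts as evaluable only if further things happen: the patient must have had a cycle of therapy, and must have a marrow at 24 weeks. For Arm D the therapy condition comes entirely after the control measurement.

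If those later events are related to treatment or to DTC burden, the evaluable 3-month comparison no longer compares the groups as randomised. Toxicity could remove patients from the drug arms, and reluctance to start therapy could remove them from Arm D. The documents give no data on either, so this is a possible mechanism and not an established bias. At stake are the only comparison with an untreated randomised group and the evaluable response rate that section 11.1.2 carries into the phase III decision.

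**Working it through.** **Inputs.** 15 patients per arm; success at 3 or more responders of 15 (section 12.2.2), or at 20% or more of patients (section 11.2.2); null response rate 4%, target 20%, stated power about 80% (section 12.2.2). The number of patients with a 3-month but no 24-week marrow is not given. I assume 0 to 4 of 15 per arm.

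**Step 1: the plan's own figure.** With X binomial, P(X ≥ 3 | 15, 0.04) = 0.020 and P(X ≥ 3 | 15, 0.20) = 0.602. The stated power of about 80% is not reproduced by this rule. That is a separate matter and is no evidence for or against the present point.

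**Step 2: the rule applied to patients.** All have DTCs at baseline and a valid 3-month marrow.

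| Patient | Therapy condition | 24-week marrow | Evaluable |
|---|---|---|---|
| Arm A–C, stops in cycle 4, 24-week marrow obtained | met | yes | yes |
| Arm A–C, stops in cycle 4, no 24-week marrow | met | no | no, including at 3 months |
| Arm D, observation marrow done, never starts therapy | not met | none on therapy | no |
| Arm D, starts therapy, no 24-week marrow | met if one cycle received | no | no |

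In the last three rows, later events decide the status of a 3-month result already in hand.

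**Step 3: timing.** If 24 weeks means weeks of therapy, the qualifying marrow comes 24 − 12 = 12 weeks after the 3-month marrow in Arms A–C, but 24 weeks after the control marrow in Arm D. If it means weeks from randomisation, Arm D is then at 24 − 12 = 12 weeks of therapy, the end of cycle 3. The text does not say which.

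**Step 4: effect on the response rate and the success rule.** The rate column assumes 3 responders and that all patients lost are non-responders. The required count is 0.2n rounded up. The false-success rate is 1 − [0.96ⁿ + n(0.04)(0.96ⁿ⁻¹) + ½n(n−1)(0.04²)(0.96ⁿ⁻²)]. The last column is P(X ≥ 3 | n, 0.20), which assumes loss unrelated to response.

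| n evaluable | 3/n | Responders needed at 20% | False success at 4% | Power at 20% |
|---|---|---|---|---|
| 15 | 20.0% | 3 | 2.0% | 60.2% |
| 14 | 21.4% | 3 (2.8 rounded up) | 1.7% | 55.2% |
| 13 | 23.1% | 3 (2.6) | 1.4% | 49.8% |
| 12 | 25.0% | 3 (2.4) | 1.1% | 44.2% |
| 11 | 27.3% | 3 (2.2) | 0.8% | 38.3% |

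The apparent rate rises, but the success decision is unchanged: 3 responders pass in every row. The false-success rate falls.

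**Step 5: the 3-month contrast, if it were confined to the evaluable set.** For a 1 SD difference, two-sided 0.05, exact t-test, any treatment against Arm D has power 0.910 at 45 against 15, and 0.801 at 33 against 11 (4 lost per arm). These are nominal sizes under equal allocation. Amendment 7 closes Arm C and redirects its later patients to Arm D, so actual sizes will differ.

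**The case against.** The strongest reply is that nothing is lost from the trial. Section 11.1.2 itself promises an intent-to-treat report, section 11.2.2 says that response is assessed in all patients, and the SAP's by-visit model can use a C3 count without a later one. This stands: the results leave one of two reported sets. A reader might infer that valid 3-month data are thrown away, and the documents do not support that.

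Second, it can be argued that section 11.1.2 does not govern the 3-month contrast at all. It concerns response, which is tied to treatment time points, whereas the contrast in section 2.2.2 is a change in DTCs with no evaluability condition. This also has force. The text never says in which set the contrast is to be run. The point therefore applies to any evaluable-set analysis of 3-month results, which the present wording does not rule out.

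Third, a reader might infer that the evaluable set consists of patients who completed treatment. It does not. One cycle is enough, and section 7.8 says that patients who stop early are still followed for outcomes. Sections 5.1 and 5.3 tie the marrow to the end of cycle 6 and do not settle whether such patients have one. The set is those with a 24-week assessment.

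Finally, a restricted evaluable set beside intent-to-treat is an accepted choice for a secondary endpoint in a feasibility pilot. That is fair, but it does not justify making a 3-month result depend on a 24-week visit.

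**Conclusion.** The point holds as a defect of definition. Followed literally, section 11.1.2 makes evaluability at 3 months depend on events after 3 months, and for Arm D it requires therapy for a measurement meant to be untreated. The evaluable response rate then describes only patients with a 24-week assessment. It matters because that population is used alongside intent-to-treat to judge activity.

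The size is unknown, because the documents give no loss rate. Under the assumption of 1 to 4 patients lost per arm, all non-responders, 3 responders of 15 read as 21% to 27% instead of 20%.

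Two stronger readings should be resisted. A reader might take the feasibility limit of 11 of 15 as a measure of missing marrows. That limit counts patients who finish six cycles free of grade 3 or 4 toxicity, so someone with such an event who finishes cycle 6 fails it and can still have the marrow. A reader might also infer that the rule makes false success more likely. With 11 to 14 evaluable it does not. The 20% rule drops to 2 responders at 10 evaluable, where P(X ≥ 2 | 10, 0.04) = 5.8%, but nothing in the documents points to a loss of that size.

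**What to change.** Reword section 11.1.2 so that evaluability is set per visit: at least 1 DTC at baseline and a marrow at the visit in question. Apply the one-cycle condition to on-treatment visits only, and not to the Arm D end-of-observation marrow. State that the 3-month contrast in section 2.2.2 uses all patients with a baseline and a 3-month marrow, whatever happens afterwards.

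The cost is the rewording, evaluable denominators that differ by visit and must be reported with each rate, and possibly slightly less favourable response rates. No new data are needed. How missing marrows count in the intent-to-treat report is also undefined, but that is a separate question which this change does not answer.
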